**Medtronic Confidential**

### 10.2.3. Classification of Serious Adverse Events

Any event that meets the SAE criteria provided in **Table 1: Adverse event definitions for reporting requirements** is to be classified as a serious adverse event (SAE).

### 10.2.4. Classification of Causal Relationships

For each observed AE, the causal relationship between the AE and the TPV, the AE and the DS, and the AE and the implant procedure will be categorized as: causal relationship, probable relationship, possible relationship, unlikely relationship, and not related, according to the definitions provided below. It should be assumed there is a causal or probable relationship to the TPV, DS, or implant procedure unless another cause is identified as a possibility.

Causal Relationship	
The event is associated with the TPV, DS, or implant procedure when:
 
 
• the event is a known side effect of the product category the TPV or DS belongs to or of similar devices and procedures;
 
• the event has a temporal relationship with TPV or DS use/application or implant procedure;
 
• the event involves a body-site or organ that             
 
○ the TPV, DS, or implant procedure are applied to;
 
○ the TPV, DS, or implant procedure have an effect on;
 
 
 
• the event follows a known response pattern to the TPV, DS, or implant procedure (if the response pattern is previously known);
 
• the discontinuation of TPV or DS application (or reduction of the level of activation/exposure) and reintroduction of its use (or increase of the level of activation/exposure) has an impact on the event (when clinically feasible);
 
• other possible causes (e.g. an underlying or concurrent illness/ clinical condition or/and an effect of another device, drug or treatment) have been adequately ruled out;
 
• harm to the subject is due to error in use.
 
 
Note: In order to establish the relatedness, not all the criteria listed above might be met at the same time, depending on the type of investigational device/implant procedure and the event.

Probable Relationship	
The relationship with the use of the TPV, DS, or implant procedure seems relevant and/or the event cannot be explained by another cause, but additional information may be obtained.

Possible Relationship	
The relationship with the use of the TPV, DS, or implant procedure is weak but cannot be ruled out completely. Alternative causes are also possible (e.g. an underlying or concurrent illness/ clinical condition or/and an effect of another device, drug or treatment).

*Medtronic Confidential*

Cases where relatedness cannot be assessed or no information has been obtained should also be classified as possible.

**Unlikely Relationship** The relationship with the use of the TPV, DS, or implant procedure seems not relevant and/or the event can be reasonably explained by another cause, but additional information may be obtained.

**Not related** Relationship to the TPV, DS, or implant procedure can be excluded when:

- the event is not a known side effect of the product category the device belongs to or of similar devices and procedures;
- the event has no temporal relationship with the use of the investigational device or the procedures;
- the serious event does not follow a known response pattern to the medical device (if the response pattern is previously known) and is biologically implausible;
- the discontinuation of medical device application or the reduction of the level of activation/exposure - when clinically feasible - and reintroduction of its use (or increase of the level of activation/exposure), do not impact on the serious event;
- the event involves a body-site or an organ not expected to be affected by the device or procedure;
- the serious event can be attributed to another cause (e.g. an underlying or concurrent illness/ clinical condition, an effect of another device, drug, treatment or other risk factors);
- harms to the subject are not clearly due to use error;
- In order to establish the non-relatedness, not all the criteria listed above might be met at the same time, depending on the type of device/procedures and the serious event.

## 10.2.5. Reporting of Device Deficiencies

Device deficiency information will be collected throughout the study and reported to Medtronic. Device deficiencies that led to an AE are reported on the AE eCRF. Device deficiencies that did not lead to an AE should be reported on a Device Deficiency eCRF (one for each device deficiency).

---

When the event is not a known side effect of the product category the device belongs to or of similar devices and procedures, it generally is considered "not related". Yet, the unexpected effect shall not be excluded from evaluation and reporting.

## 10.3. Anticipated Adverse Events

Anticipated AEs for subjects participating in the study are outlined in Section 9.1. Potential Risks. Further information is provided in the Investigator's Brochure and IFU.

## 10.4. Emergency Contact Details for Reporting SAE, UADE, and Device Deficiencies

Investigators should contact the Medtronic study manager or site manager if they have any questions regarding reportable AEs. Medtronic will maintain a listing of current study contact details and provide to each site

## 11. Data Review Committees

### 11.1. Screening Committee

- A Screening Committee will be used to ensure patient selection is appropriate and consistent among trial sites. The role of the Screening Committee will include the following: Confirmation that subjects meet inclusion / exclusion criteria
- Confirmation that subjects are anatomically suitable for Harmony TPV implant

The Screening Committee will be comprised of a subset of study investigators with expertise including:

- Congenital Heart Disease
- Interventional Cardiology
- Cardiac Surgery
- Cardiac Imaging

### 11.2. Clinical Events Committee

A Clinical Events Committee (CEC) will provide independent medical review and adjudication of adverse event data used in the safety assessment of the investigational device. The CEC will adjudicate, at a minimum, all deaths and endpoint related adverse events, as outlined in the CEC charter. Any related source documentation provided to the Sponsor for CEC review and adjudication will be de-identified. All efforts should be made by the PI to provide source documentation for review as requested by the CEC. In the event source documentation cannot be obtained, a summary of the event and related clinical findings may be provided by the PI.

The analysis of the study safety data will be based on CEC adjudications. The CEC members will be free from bias towards the study and will be independent from the study investigators and Medtronic. The committee will consist of at least 3 independent experts (non-Medtronic employed physicians) with expertise relevant to the study. This may include experience in the areas of:

*Medtronic Confidential*

- Congenital Heart Disease
- Interventional Cardiology
- Cardiac Surgery

## 11.3. Data Monitoring Committee

A Data Monitoring Committee (DMC) will assess interim study data and provide recommendations to Medtronic regarding study conduct, should they identify any issues that may affect the safety of the study subjects. DMC members will be free from bias towards the study and will be independent from the study investigators, and Medtronic. The DMC will consist of a minimum of 3 members who may have experience in the areas of:

- Congenital Heart Disease
- Interventional Cardiology
- Cardiac Surgery

The DMC will meet (via teleconference or in person) to establish procedures for safety data review, chair appointment, and guidelines for study recommendations. The DMC will meet on a periodic basis to perform a comprehensive data review, including at a minimum, all SAEs and deaths, and will meet more frequently when needed. Safety-related endpoints may also be reviewed at these meetings. DMC meetings may consist of both open and closed sessions. Medtronic personnel may facilitate the DMC meeting but will not have voting privileges.

Following each meeting, the DMC will report to Medtronic in writing and may recommend changes in the conduct of the study. The DMC recommendations may include recommendations on study status such as continuing the study without modifications, continuing the study with modifications, stopping or suspending enrollment, or recommendations regarding study conduct including recommendations around enrollment or protocol deviations.

In the case of UADEs, if Medtronic and the DMC determine that the event presents an unreasonable risk to the participating subjects, Medtronic must terminate the clinical study within 5 working days after making that determination and no later than 15 working days after Medtronic first receives notice of the effect. All study sites will be notified of this action.

The DMC may call additional meetings if, at any time, there is concern about any aspect of the study. All data presented at the meetings will be considered confidential.

*Medtronic Confidential*

## 12. Statistical Design and Methods

The primary analysis for safety and effectiveness will be performed when the first 40 implanted subjects have completed their 6-month follow-up. A supplemental analysis will be performed when the 10 US implants of mTPV 25 cohort have completed their 1-month follow-up. Both cohorts will be pooled for additional analysis out to 5 years after the previously mentioned analyses are completed.

### 12.1. Analysis Sets

The analysis subsets are defined as follows:

#### Enrolled Cohort

The enrolled cohort consists of all enrolled subjects. Subjects are considered enrolled at the point of signing the Informed Consent Form.

#### Catheterized Cohort

The catheterized cohort consists of all subjects who undergo catheterization for possible implantation of the Harmony TPV.

#### Attempted Implant Cohort

The attempted implant cohort consists of all subjects who undergo catheterization and a Harmony TPV implantation was attempted (Harmony TPV is introduced into the subject's body).

#### Implanted Cohort

The implanted cohort consists of all subjects who undergo catheterization and a Harmony TPV was implanted.

#### Implanted > 24 hours Cohort

The implanted >24 hours cohort consists of all subjects who have a Harmony TPV implanted which remains implanted for greater than 24 hours.

### 12.2. Primary Objectives

The primary objectives are descriptive, and no statistical hypothesis test will be performed. There is no sample size calculation for the primary objectives. The analysis population will include data from this study in combination with the data from the Native Outflow Tract Transcatheter Pulmonary Valve Research Clinical Study (IDE #G120175).

---

 While the primary safety endpoint is measured at 30 days, primary objective analysis will be completed upon completion of the primary efficacy endpoint, which is measured at 6 months.

The analysis for primary objectives will be performed when all subjects have reached their 6-month endpoint.

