Additional Outcome Measures	
 
• Technical success at exit from catheterization lab/operating room
 
• Device success out to 5 years
 
• Procedural success at 30 days
 
• Freedom from TPV dysfunction out to 5 years
 
• Assessment of safety
 
• Characterize quality of life scores over time
 
• Characterize right ventricle remodeling following TPV implant
 
• Confirmation of the procedural feasibility, hemodynamic performance and safety profile of Harmony TPV 25 (roll-in cohort)
 
• Confirmation of the procedural feasibility, hemodynamic performance and safety profile of the modified TPV 25 (10 US implants)
 

Study Design	Multi-center, prospective, non-randomized, interventional, investigational
Investigative Sites	Up to 15 investigational sites in the United States, Canada, and Japan
Sample Size	
 
• Pivotal cohort: Primary analysis for up to 40 subjects implanted including the Harmony TPV 25 Roll-In cohort
 
• Additional analysis for the Harmony modified TPV 25 (mTPV 25) cohort: ten subjects implanted in the United States, and up to five subjects implanted in Canada and/or Japan
 

Patient Population	Patients who have congenital heart disease and are clinically indicated for pulmonary valve replacement.

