## 12.2.1. Primary Safety Endpoint

The primary safety endpoint is freedom from procedure or device-related mortality.

CEC adjudicated data will be used to assess the safety endpoint.

The analysis cohort will be the catheterized cohort. The endpoint will be described by Kaplan-Meier statistics. The loglog transformed two-sided 95% confidence interval using the Peto standard error at 30 days will be presented. The primary safety objective will be met if the point estimate of the freedom from procedure or device-related mortality rate at 30 days post-procedure is equal to or greater than the performance target of 95%.

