## 12.2.2. Primary Efficacy Endpoint

The primary efficacy endpoint is percentage of subjects with acceptable hemodynamic function composite at 6 months as defined by:

- Mean RVOT gradient as measured by continuous-wave Doppler echocardiography  $\leq 40$  mmHg
  - If a catheterization is performed for clinical purposes, the catheterization peak gradient measurement will supersede the continuous-wave Doppler echocardiography measurement and be used to support the primary endpoint. Acceptable hemodynamic function as measured by catheterization will be considered to be peak gradient  $\leq 40$  mmHg.

-AND-

- Pulmonary regurgitant fraction as measured by magnetic resonance imaging  $< 20\%$ 
  - If magnetic resonance imaging is contraindicated, a continuous-wave Doppler echocardiography measurement will be used to support the primary endpoint. Acceptable hemodynamic function as measured by continuous-wave Doppler echocardiography will be considered to be  $<$  moderate pulmonary regurgitation.

Core lab data will be used to assess the efficacy endpoint, with an exception in the case that a catheterization is performed to measure mean RVOT gradient, in which site reported data will be utilized.

---

 While the primary safety endpoint is measured at 30 days, primary objective analysis will be completed upon completion of the primary efficacy endpoint, which is measured at 6 months.

The analysis cohort for the primary efficacy endpoint will be the implanted > 24 hours cohort. The percentage of subjects with acceptable hemodynamic function at 6 months and a two-sided 95% Clopper-Pearson interval will be provided. The primary efficacy objective will be met if the point estimate is equal to or greater than the performance target of 75%.

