#### 3. Introduction

This document outlines the detailed statistical methods to be implemented for the data collected within the scope of the Medtronic Coronary and Structural Heart (CSH) Harmony Transcatheter Pulmonary Valve (TPV) in patients who have congenital heart disease and are clinically indicated for pulmonary valve replacement. The purpose of this plan is to provide a framework which answers the study objectives in a statistically rigorous fashion, without bias or analytical deficiencies.

Specifically, this Statistical Analysis Plan (SAP) has the following purpose: to prospectively (a priori) outline the types of analyses and presentations of data that will form the basis for conclusions to be reached that will answer the study objectives outlined in the protocol, and to explain in detail how the data will be handled and analyzed, adhering to commonly accepted standards and practices of statistical analysis in the medical device industry.

The primary analysis for safety and effectiveness will be performed when the first 40 implanted subjects (including Roll-in TPV 25 subjects) have completed their 6-month follow-up. While the primary safety endpoint is measured at 30 days, primary objective analysis will be completed upon completion of the primary efficacy endpoint, which is measured at 6 months. Following the completion of the 40 pivotal cohort of the TPV 22 and TPV 25, the TPV 25 was modified and is referred to as modified TPV 25 (mTPV 25). A supplemental analysis will be performed when the 10 US implants of modified TPV 25 (mTPV 25) cohort have completed their 1-month follow-up for both safety and efficacy. Both cohorts will be pooled for additional analysis out to 5 years after the previously mentioned analyses are completed. Hence the primary efficacy endpoint analysis for PMA will not include the mTPV 25 cohort due to those subjects not being eligible for their 6-month visit at the time of PMA snapshot. Once all subjects from both cohorts finish their 6-month visit, the endpoint analysis will be repeated on all subjects.

The analysis population for the Harmony PMA will include subjects from the Harmony Pivotal Study in combination with the data from the Native Outflow Tract Transcatheter Pulmonary Valve Research Clinical Study (IDE #G120175). Note the Native study only includes TPV22 implants.

Revision 5.1 Page 8 of 24

Form Medtronic

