#### 6. Determination of Sample Size

There is no sample size calculation for the primary objectives. The primary analysis will include 40 pivotal cohort of the TPV 22 and TPV 25. For the modified TPV 25 (mTPV 25), an additional cohort of up to 15 subjects implanted with the mTPV 25 (10 US implants and up to 5 OUS implants from Canada and/or Japan).

The pooled analysis cohort will include data from this study in addition to the data from the Native Outflow Tract Transcatheter Pulmonary Valve Research Clinical Study (IDE #G120175, n=20).

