#### 7.9.1.2 Data Collection and Analysis Methods

CEC adjudicated data will be used to assess the safety endpoint. The analysis cohort will be the catheterized cohort. The endpoint will be described by using Kaplan-Meier method. The loglog transformed two-sided 95% confidence interval using the Peto standard error at 30 days will be presented. The primary safety objective will be met if the point estimate of the freedom from procedure or device-related mortality rate at 30 days post-procedure is equal to or greater than the performance target of 95%.

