#### 7.9.2.2 Data Collection and Analysis Methods

Core lab data will be used to assess the efficacy endpoint, with an exception in the case that a catheterization is performed to measure mean RVOT gradient, in which site reported data will be utilized. The analysis cohort for the primary efficacy endpoint will be the implanted > 24 hours cohort. The percentage of subjects with acceptable hemodynamic function at 6 month and a two-sided 95% Clopper-Pearson confidence interval will be provided. The primary efficacy objective will be met if the point estimate is equal to or greater than the performance target of 75%.

The efficacy endpoint will be assessed using the 6-month echo, diagnostic catheterization performed during the 6-month protocol window, and reintervention status through 6 months. If 6-month echo occurred prior to 6-month time window opening or missed, next available echo that is after the 6-month window opening will be used, unscheduled or 1-year echo, which ever came first. Tables below define success or failure for all possible scenarios. Only subjects whose procedure were 6 months prior will be included in the analysis. Modified TPV 25 subjects will be excluded from the primary analysis for PMA. The primary endpoint will be evaluated again when all subjects reach 6-month visit.

Previous Reinterventions or Diagnostic Catheterization Procedures			
	6-Month Echo Not Performed or Evaluable	6-Month Echo Acceptable Hemodynamics	6-Month Echo Unacceptable Hemodynamics
Any Harmony Reintervention Prior to 6-Month Window Closing	Fail	Fail	Fail
Diagnostic Cath Acceptable Hemodynamics Prior to 6- Month Window	Not Evaluable	Success	Fail
Diagnostic Cath Acceptable Hemodynamics During 6- Month Window	Success	Success	Success
Diagnostic Cath Unacceptable Hemodynamics Prior to 6- Month Window	Not Evaluable	Success	Fail
Diagnostic Cath Unacceptable Hemodynamics During 6- Month Window	Fail	Fail	Fail

Revision 5.1 Page 17 of 24

No Previous Reinterventions or Diagnostic Catheterization Procedures			
	6-Month Echo Not Performed or Evaluable	6-Month Echo Acceptable Hemodynamics	6-Month Echo Unacceptable Hemodynamics
Previous Echo Acceptable Hemodynamics	Not Evaluable	Success	Fail
Previous Echo Unacceptable Hemodynamics	Not Evaluable	Success	Fail

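### Protocol 12.2 pools in the feasibility study for the primary objectives, the Protocol synopsis and SAP 6 make the 40 pivotal subjects primary, and nothing says which estimate is held against 95% and 75%

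*Protocol*

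**What the plan says.** **Pooled.** Protocol 12.2, on the primary objectives: "The analysis population will include data from this study in combination with the data from the Native Outflow Tract Transcatheter Pulmonary Valve" study. The decision rules sit in its two subsections. In 12.2.1 safety is met if the point estimate "is equal to or greater than the performance target of 95" per cent. In 12.2.2: "The primary efficacy objective will be met if the point estimate is equal to or greater than the performance target of 75" per cent. SAP 3 describes the population for the marketing application in the same way: "The analysis population for the Harmony PMA will include subjects from the Harmony Pivotal Study in combination with the data from the Native" study.

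**The 40.** The Protocol synopsis, under sample size: "Primary analysis for up to 40 subjects implanted including the Harmony TPV 25 Roll-In cohort". SAP 6: "The primary analysis will include 40 pivotal cohort of the TPV 22 and TPV 25". SAP 6 then names a pooled cohort separately, adding the feasibility study at n=20. SAP 5 and Protocol 8.4 place the roll-in and later TPV 25 subjects in a 40-subject cohort.

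**Silent on the choice.** SAP 7.9.1.2 repeats the safety rule ("The primary safety objective will be met if the point estimate of the freedom from procedure or device-related mortality rate at 30 days" reaches 95%) and SAP 7.9.2.2 repeats the efficacy rule. They name the catheterized and implanted >24 hours cohorts, which are defined by procedure status and not by study. SAP 7.13 lists both primary endpoints for pooled analysis but gives no target. SAP 7.14, on changes to the planned analysis, records only the added reintervention criterion.

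**The concern.** Each primary objective is declared met or not met by a bare point estimate against a fixed target. With such a rule the denominator is part of the rule. Here the text supports two denominators for one verdict, about 40 and about 60, so two analysts who each follow the documents could report opposite conclusions from the same data.

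Even when the verdicts agree, the headline estimate and its interval differ. The device mix differs too, because the SAP notes that the feasibility study contains TPV 22 implants only.

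**Working it through.** The plan gives no sample size, power or alpha to reproduce; the objectives are descriptive. The check applies the stated rules to each candidate population.

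**Inputs.** Pivotal n = 40 (Protocol synopsis, SAP 6). Feasibility n = 20 (SAP 6). Pool = 40 + 20 = 60. Targets 95% and 75% (Protocol 12.2.1 and 12.2.2).

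**Assumptions.** All 40 and all 20 are evaluable. For safety the same numbers stand in for the catheterized cohorts, whose sizes are not given. There is no censoring before day 30, so the Kaplan-Meier estimate equals the simple proportion.

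**Thresholds.**
- Efficacy, minimum successes: 0.75 × 40 = 30; 0.75 × 60 = 45.
- Safety, maximum related deaths: 0.05 × 40 = 2; 0.05 × 60 = 3.

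**Opposite verdicts.**
- 29/40 = 72.5%, not met. With 16/20 in the feasibility study, 45/60 = 75.0%, met. The Clopper-Pearson 95% intervals are 56.1% to 85.4% and 62.1% to 85.3%, so the verdict turns on results that are hardly distinguishable.
- 30/40 = 75.0%, met. With 14/20, 44/60 = 73.3%, not met.
- 3 deaths in 40: 37/40 = 92.5%, not met. With none in the 20, 57/60 = 95.0%, met.
- 2 deaths in 40: 38/40 = 95.0%, met. With 2 in the 20, 56/60 = 93.3%, not met.

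**Dependence on the feasibility result.** With y successes in the 20, the pool needs 45 − y from the pivotal 40, against 30 when the 40 stand alone. At y = 15 the two rules coincide (45 − 15 = 30). Above 15 the pool is the easier test; below 15 it is the harder one.

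**How often verdicts differ.** Let X ~ Bin(40, p) and Y ~ Bin(20, p) be independent. Sum P(X = x)·P(Y = y) over all pairs where exactly one rule is satisfied: x ≥ 30 against x + y ≥ 45 for efficacy, and x ≥ 38 against x + y ≥ 57 survivors for safety.

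| Endpoint | True rate | Only the 40 meet | Only the pool meets | Verdicts differ |
|---|---|---|---|---|
| Efficacy | 70% | 11.6% | 5.1% | 16.8% |
| Efficacy | 75% | 10.2% | 8.6% | 18.8% |
| Efficacy | 80% | 4.0% | 7.0% | 11.0% |
| Efficacy | 85% | 0.5% | 2.1% | 2.6% |
| Efficacy | 90% | <0.1% | 0.1% | 0.1% |
| Safety | 95% | 9.6% | 6.6% | 16.2% |
| Safety | 97% | 3.5% | 4.7% | 8.2% |
| Safety | 98% | 1.2% | 2.5% | 3.7% |
| Safety | 99% | 0.1% | 0.6% | 0.7% |

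(Totals are from unrounded values.)

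**Other denominators.** With 36 and 18 evaluable (27 and 41 successes needed), efficacy verdicts differ in 11.9% at 80%, 3.1% at 85% and 0.2% at 90%. With catheterized cohorts of 45 and 22 (still 2 and 3 deaths allowed), safety verdicts differ in 17.3%, 9.9%, 4.7% and 0.9% at 95%, 97%, 98% and 99%. The picture does not change.

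**The case against.** The strongest reply is that the SAP already answers the question. SAP 6 separates the primary analysis from the pooled cohort, SAP 5 speaks of a 40-subject analysis cohort, the met rules sit in 7.9, and pooling has its own section, 7.13, with no target. On that view one sentence in Protocol 12.2 was simply left unaligned. Much of this stands: a reader might infer that the question is wholly open, and the documents do not support that. But the preference for the 40 is an inference. It contradicts the wording of Protocol 12.2, and SAP 7.14 does not record it as a change. SAP 7.9.2.2 also ties its primary analysis to the marketing application, whose population SAP 3 defines as pooled.

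Second, the synopsis and SAP 6 entries are sample-size statements that contrast the pivotal and mTPV 25 cohorts; neither expressly excludes feasibility data. That is fair, and it makes the conflict one of unclear wording more than of two opposed rules. The verdict still lacks a stated denominator.

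Third, a reader might infer an inflated type I error or an analysis that was never planned. Neither follows. No hypothesis is tested, confidence intervals accompany the estimates, and both the 40-subject and the pooled results are in the plan. What is missing is the label that says which one decides.

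Fourth, the disagreement rates are not forecasts. Protocol 5.2 and 9.3 treat feasibility results as already available, so a fresh draw of 20 is illustrative only, and the documents give no expected rates that place the trial near its targets. This stands.

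Finally, SAP 7.9.2.2 adds a later repeat: "The primary endpoint will be evaluated again when all subjects reach 6-month visit". A reader might see in it a third contender for the decision. SAP 3 and 7.9.2.2 place it after the primary analysis, so it needs no restriction here.

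**Conclusion.** The inconsistency holds and should be corrected. Protocol 12.2 and the synopsis with SAP 6 give different populations for the same primary decision, and no section says which estimate is compared with 95% and 75%. The balance of the text favours the 40 without settling it.

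The consequence depends on where the true rates lie: roughly one trial in six at the safety target and nearly one in five at the efficacy target, falling to 0.7% at 99% safety and 0.1% at 90% efficacy. These figures assume equal true rates in the two studies, full cohorts of 40 and 20, no early censoring and a feasibility result not yet known. The contradiction in the text and the count examples need neither the equal-rate assumption nor the unknown feasibility result.

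**What to change.** Amend the population sentence in Protocol 12.2, and add one sentence to SAP 7.9, to name the single population whose point estimate is compared with 95% and 75%. The 40-subject pivotal cohort is the choice most consistent with the Protocol synopsis and SAP 5 and 6. Label the other result as supportive; if the 40 are chosen, that is the pooled result in SAP 7.13. Record the alignment in SAP 7.14.

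Protocol 5 says that the 40-subject cohort is complete, but the documents do not say whether its results have been read. If they have, report both results and state when the deciding population was chosen.

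The cost is a few sentences, with no new data, visits or subjects. The drawback of choosing the 40 is that the decision rests on fewer subjects.
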